Appendix 2. Clinical Laboratory Tests (Fasting)

Hematology	Clinical Chemistry
Hematocrit	Sodium
Hemoglobin	Potassium
Erythrocyte count (RBC)	Bicarbonate
Mean cell volume	Chloride
Mean cell hemoglobin	Calcium
Mean cell hemoglobin concentration	Phosphorus
Leukocytes (WBC)	Magnesium
Platelets	Glucose
	Creatinine
Differential WBC (absolute counts of):	Blood urea nitrogen (BUN)
Neutrophils	Uric acid
Lymphocytes	Total cholesterol
Monocytes	Total protein
Eosinophils	Albumin
Basophils	Total bilirubin ^d
Urinalysis ^e	Alkaline phosphatase (ALP)
Specific gravity	Aspartate aminotransferase (AST)
pH	Alanine aminotransferase (ALT)
Protein	Creatine Phosphokinase
Glucose	Gamma-glutamyl transferase (GGT)
Ketones	Ethanol testing ^{a,b}
Bilirubin	Urine drug screen ^{a,b}
Urobilinogen	Hepatitis B surface antigen ^a
Blood	Hepatitis C antibody ^a
Nitrite	HIV ^a
	Pregnancy test
	FSH ^{a,c}
	Thyroid-stimulating hormone ^a

Abbreviations: FSH = follicle-stimulating hormone; HIV = human immunodeficiency virus; RBC = red blood cell; WBC = white blood cell.

^a Performed at screening only.

^b Urine drug screen and ethanol level may be repeated prior to admission to the clinical research unit and at other times indicated in the Schedule of Activities.

^c Performed in 40- to 55-year old females to confirm their post-menopausal status. In males, FSH will be collected at screening and at other times indicated in the Schedule of Activities, as part of testicular hormonal function assessment.

^d Reflex test will be done if abnormalities are noted.

^e Reflex microscopy will be done if abnormalities are noted.

Appendix 3. Study Governance, Regulatory and Ethical Considerations

Informed Consent

The investigator is responsible for

- ensuring that the subject understands the nature of the study, the potential risks and benefits of participating in the study, and that their participation is voluntary.
- ensuring that informed consent is given by each subject or legal representative. This includes obtaining the appropriate signatures and dates on the ICF prior to the performance of any protocol procedures and prior to the administration of investigational product.
- answering any questions the subject may have throughout the study and sharing in a timely manner any new information that may be relevant to the subject's willingness to continue his or her participation in the study.
- providing a copy of the ICF to the participant or the participant's legal representative and retaining a copy on file.

Recruitment

Lilly or its designee is responsible for the central recruitment strategy for subjects. Individual investigators may have additional local requirements or processes. Study-specific recruitment material should be approved by Lilly.

Ethical Review

The investigator or appropriate local representative must give assurance that the ethical review board (ERB) was properly constituted and convened as required by ICH guidelines and other applicable laws and regulations.

Documentation of ERB approval of the protocol and the ICF must be provided to Lilly before the study may begin at the investigative site(s). Lilly or its representatives must approve the ICF before it is used at the investigative site(s). All ICFs must be compliant with the ICH guideline on GCP.

The study site's ERB(s) should be provided with the following:

- the current IB and updates during the course of the study
- ICF
- relevant curricula vitae

Regulatory Considerations

This study will be conducted in accordance with the protocol and with

- 1) consensus ethics principles derived from international ethics guidelines, including the Declaration of Helsinki and Council for International Organizations of Medical Sciences International Ethical Guidelines
- 2) applicable ICH GCP Guidelines
- 3) applicable laws and regulations

Some of the obligations of the sponsor will be assigned to a third-party organization.

Protocol Signatures

The sponsor's responsible medical officer will approve the protocol, confirming that, to the best of his or her knowledge, the protocol accurately describes the planned design and conduct of the study.

After reading the protocol, each principal investigator will sign the protocol signature page and send a copy of the signed page to a Lilly representative.

Final Report Signature

The investigator or designee will sign the clinical study report for this study, indicating agreement with the analyses, results, and conclusions of the report.

The sponsor's responsible medical officer and statistician will sign/approve the final clinical study report for this study, confirming that, to the best of his or her knowledge, the report accurately describes the conduct and results of the study.

Data Quality Assurance

To ensure accurate, complete, and reliable data, Lilly or its representatives will do the following:

- provide instructional materials to the study sites, as appropriate.
- provide training to instruct the investigators and study coordinators. This training will give instruction on the protocol, the completion of the CRFs, and study procedures.
- make periodic visits to the study site.
- be available for consultation and stay in contact with the study site personnel through mail, telephone, and/or fax.
- review and evaluate CRF data and/or use standard computer edits to detect errors in data collection.
- conduct a quality review of the database.

In addition, Lilly or its representatives will periodically check a sample of the subject data recorded against source documents at the study site. The study may be audited by Lilly and/or regulatory agencies at any time. Investigators will be given notice before an audit occurs.

The investigator will keep records of all original source data. This might include laboratory tests, medical records, and clinical notes. If requested, the investigator will provide the sponsor,

applicable regulatory agencies, and applicable ERBs with direct access to the original source documents.

Data Collection Tools/Source Data

An electronic data capture system will be used in this study. The site must define and retain all source records and must maintain a record of any data where source data are directly entered into the data capture system.

Data Protection

Data systems used for the study will have controls and requirements in accordance with local data protection law.

The purpose and use of subject personal information collected will be provided in a written document to the subject by the sponsor.

Study and Site Closure

Discontinuation of Study Sites

Study site participation may be discontinued if Lilly or its designee, the investigator, or the ERB of the study site judges it necessary for medical, safety, regulatory, or other reasons consistent with applicable laws, regulations, and GCP.

Discontinuation of the Study

The study will be discontinued if Lilly or its designee judges it necessary for medical, safety, regulatory, or other reasons consistent with applicable laws, regulations, and GCP.

Appendix 4. Hepatic Monitoring Tests for Treatment-Emergent Abnormality

Selected tests may be obtained in the event of a treatment-emergent hepatic abnormality and may be required in follow-up with patients in consultation with Lilly or its designee CRP.

Hepatic Monitoring Tests

Hepatic Hematology^a

Hemoglobin

Hematocrit

RBC

WBC

Neutrophils

Lymphocytes

Monocytes

Eosinophils

Basophils

Platelets

Haptoglobin^a

Hepatic Coagulation^a

Prothrombin time

Prothrombin time, INR

Hepatic Serologies^{a,b}

Hepatitis A antibody, total

Hepatitis A antibody, IgM

Hepatitis B surface antigen

Hepatitis B surface antibody

Hepatitis B core antibody

Hepatitis C antibody

Hepatitis E antibody, IgG

Hepatitis E antibody, IgM

Anti-nuclear Antibody^a

Alkaline Phosphatase Isoenzymes^a

Anti-smooth Muscle Antibody (or Anti-actin Antibody)^a

Abbreviations: ALT = alanine aminotransferase; AST = aspartate aminotransferase; CPK = creatinine

phosphokinase; GGT = gamma-glutamyl transferase; Ig = immunoglobulin; INR = international normalized ratio; RBC = red blood cell; TBL = total bilirubin level; WBC = white blood cell.

^a Assayed by Lilly-designated or local laboratory.

Appendix 5. Blood Sampling Summary

This table summarizes the approximate number of venipunctures and blood volumes for all blood sampling (screening, safety laboratories, and bioanalytical assays) during the study.

Protocol J2M-MC-GZKA Sampling Summary for Part A

Purpose	Blood Volume per Sample (mL)	Number of Blood Samples	Total Volume (mL)
Screening tests ^a	45	1	45
Serum pregnancy test	3.5	1	3.5
Clinical laboratory tests ^a	12	6	72
Serum creatinine	2.5	3	7.5
Pharmacokinetics	2	14	28
Pharmacodynamics, including fructose tolerance test	2	13	26
Pharmacogenetics	10	1	10
Fasting biomarker samples (nonpharmacogenetic)	11.5 (4 mL plasma; 7.5 mL serum)	2	23
CCI	3	12	36
Total			251
Total for clinical purposes (rounded up to the nearest 10 mL)			260

^a Additional samples may be drawn if needed for safety purposes.

Protocol J2M-MC-GZKA Sampling Summary for Part B (Cohorts 1 and 3)

Purpose	Blood Volume per Sample (mL)	Number of Blood Samples	Total Volume (mL)
Screening tests ^a	45	1	45
Serum pregnancy test	3.5	1	3.5
Clinical laboratory tests ^a	12	7	84
Serum creatinine	2.5	3	7.5
Testosterone, follicle-stimulating hormone, and luteinizing hormone	3.5	4	14
LY3478045 pharmacokinetics	2	23	46
Fasting insulin and adiponectin	2.5	2	5
Pharmacodynamics, including fructose tolerance test	2	26	52
Pharmacogenetics	10	1	10
Fasting biomarker samples (nonpharmacogenetic)	11.5 (4 mL plasma; 7.5 mL serum)	3	34.5
CCI [REDACTED]	3	18	54
Total			355.5
Total for clinical purposes (rounded up to the nearest 10 mL)			360

[figure not shown]
^a Additional samples may be drawn if needed for safety purposes.

Protocol J2M-MC-GZKA Sampling Summary for Part B (Cohorts 2 and 4)

Purpose	Blood Volume per Sample (mL)	Number of Blood Samples	Total Volume (mL)
Screening tests ^a	45	1	45
Serum pregnancy test	3.5	1	3.5
Clinical laboratory tests ^a	12	7	84
Serum creatinine	2.5	3	7.5
Testosterone, follicle-stimulating hormone, and luteinizing hormone	3.5	4	14
LY3478045 pharmacokinetics	2	32	64
Fasting insulin and adiponectin	2.5	2	5
Pharmacodynamics, including fructose tolerance test	2	26	52
CCI [REDACTED]	2	24	48
Pharmacogenetics	10	1	10
Fasting biomarker samples (nonpharmacogenetic)	11.5 (4 mL plasma; 7.5 mL serum)	3	34.5
CCI [REDACTED]	3	27	81
Total			448.5
Total for clinical purposes (rounded up to the nearest 10 mL)			450

^a Additional samples may be drawn if needed for safety purposes.

Appendix 6. Excluded Concomitant Medications

**Appendix 7. Protocol Amendment J2M-MC-GZKA(c)
Summary - A Safety, Tolerability, Pharmacokinetic, and
Pharmacodynamic Study of Single- and Multiple-
Ascending Doses of LY3478045 in Healthy Subjects**

Overview

Protocol J2M-MC-GZKA, A Safety, Tolerability, Pharmacokinetic, and Pharmacodynamic Study of Single- and Multiple-Ascending Doses of LY3478045 in Healthy Subjects, has been amended. The new protocol is indicated by Amendment (c) and will be used to conduct the study in place of any preceding version of the protocol.

The overall changes and rationale for the changes made to this protocol are as follows:

- Protocol was amended to remove sorbitol analysis from pharmacodynamic analysis section as it is an indirect biomarker. The fructose level is a direct biomarker, and its analysis was confirmed to provide robust and sufficient pharmacodynamic information.

Revised Protocol Sections

Note:

All deletions have been identified by ~~strikethroughs~~.

All additions have been identified by the use of underscore.

9.6 Pharmacodynamics

Fructose Tolerance Test: Three meals (breakfast, lunch, and dinner) will be served at approximately 20 minutes, 6 hours, and 12 hours after dose with low fructose content. A beverage containing mixture of fructose and glucose (CCI [REDACTED] in approximately 300 to 500 mL of non-caloric solution) will be served with each of the 3 meals on Day 1 in Part A (SAD) and Days 1 and 14 in Part B (MAD). The beverage should be served after a portion of the meal has been consumed. The meals should start at the defined time (20 minutes, 6 hours, and 12 hours postdose). Blood samples for the analysis of fructose and sorbitol will be collected into appropriately labeled tubes containing ethylene diamine tetra acetic acid at the time points specified in the Schedule of Activities (Section 2). Sample handling and shipment to the central laboratory will occur per instructions given to the study site.

Signature Page for VV-CLIN-002394 v1.0

Approval	PPD
	10-Aug-2021 20:27:10 GMT+0000

Approval	PPD
	11-Aug-2021 05:07:33 GMT+0000

Signature Page for VV-CLIN-002394 v1.0

Approved on 11 Aug 2021 GMT

2. ABBREVIATIONS

Abbreviations pertain to the Statistical Analysis Plan (SAP) only (not the tables, figures and listings [TFLs]).

%AUC($t_{last}-\infty$)	Percentage of AUC that is due to extrapolation from the last measurable concentration to infinity
ADA	Anti-drug antibody
AE	Adverse event
A_e	Amount excreted in urine
AUC	Area under the concentration versus time curve
AUC(0-6)	Area under the concentration versus time curve from time zero to 6 h.
AUC(0- t_{last})	Area under the concentration versus time curve from time zero to time t , where t is the last time point with a measurable concentration
AUC(0- ∞)	Area under the concentration versus time curve from time zero to infinity
AUC(0-24)	Area under the concentration versus time curve from time zero to 24 hours postdose
AUC(6-12)	Area under the concentration versus time curve from time 6 h to 12 h.
AUC(12-24)	Area under the concentration versus time curve from time 12 h to 24 h.
AUC τ	Area under the concentration versus time curve during one dosing interval
CI	Confidence interval
CL/F	Apparent total body clearance of drug calculated after extra-vascular administration
CL _R	Renal clearance
C _{max}	Maximum observed drug concentration
C _{predose}	Predose observed drug concentration
CRF	Case Report Form
CRU	Clinical Research Unit
CSR	Clinical Study Report
CV	Coefficient of variation
ECG	Electrocardiogram
f _e	Percentage of dose excreted in urine
FTT	Fructose Tolerance Test

ICH	International Conference on Harmonisation
MedDRA	Medical Dictionary for Regulatory Activities
MR(AUC)	Metabolite ratio based upon AUC(0-∞)
MR (C _{max})	Metabolite ratio based upon C _{max}
PD	Pharmacodynamic
PK	Pharmacokinetic
QTcF	QT interval corrected using Fridericia's formula
R _A (AUC)	Accumulation ratio based upon AUC(0-24)
R _A (C _{max})	Accumulation ratio based upon C _{max}
SAP	Statistical Analysis Plan
TFLs	Tables, Figures, and Listings
t _{max}	Time of maximum observed drug concentration
ULN	Upper limit of normal
V _{ss} /F	Apparent volume of distribution at steady state after extra-vascular administration
V _z /F	Apparent volume of distribution during the terminal phase after extra-vascular administration
WHO	World Health Organization

3. INTRODUCTION

This SAP has been developed after review of the Clinical Study Protocol (final version dated 15 January 2020), protocol amendment (a) (final version dated 04 March 2020), protocol amendment (b) (final version 09 December 2020), protocol amendment (c) (final version dated 11 August 2021), and SAP Version 1 (final version dated 29 April 2020).

This SAP describes the planned analysis of the safety, tolerability, pharmacokinetic (PK) and pharmacodynamic (PD) data from this study. A detailed description of the planned TFLs to be presented in the clinical study report (CSR) is provided in the accompanying TFL shell document.

The intent of this document is to provide guidance for the statistical analyses of data. In general, the analyses are based on information from the protocol, unless they have been modified by agreement with Eli Lilly and Company. A limited amount of information concerning this study (e.g., objectives, study design) is given to help the reader's interpretation. When the SAP and TFL shells are agreed upon and finalized, they will serve as the template for this study's CSR.

This SAP supersedes the statistical considerations identified in the protocol; where considerations are substantially different, they will be so identified. If additional analyses are required to supplement the planned analyses described in this SAP, they may be performed and will be identified in the CSR. Any substantial deviations from this SAP will be agreed upon with Eli Lilly and Company and identified in the CSR. Any minor deviations from the TFLs may not be documented in the CSR.

This SAP is written with consideration of the recommendations outlined in the International Conference on Harmonisation (ICH) E9 Guideline entitled Guidance for Industry: Statistical Principles for Clinical Trials¹ and the ICH E3 Guideline entitled Guidance for Industry: Structure and Content of Clinical Study Reports².

4. STUDY OBJECTIVES

4.1 Primary Objective

To investigate the safety and tolerability of single and multiple oral doses of LY3478045 in healthy subjects.

4.2 Secondary Objective

To determine the PK of LY3478045 following single and multiple doses in healthy subjects.

4.3 Exploratory Objectives

- To determine the PD effects of LY3478045 following single and multiple doses in healthy subjects.
- To investigate the effect of LY3478045 on the PK of CCI [REDACTED] following multiple doses in healthy subjects.

• CCI

5. STUDY DESIGN

Study GZKA is a Phase 1, single site, randomized, double-blind, placebo-controlled, 2-part study of LY3478045 in healthy subjects.

5.1 Part A

Single-ascending oral doses of either LY3478045 or placebo will be administered in up to 5 cohorts. Each cohort will consist of 8 subjects. Cohort 5 is an optional cohort that may be assessed based on the available safety and PK data from the previous cohorts. In each cohort, 6 subjects will be randomized to receive LY3478045 and 2 subjects to receive placebo.

A sentinel dosing strategy will be utilized for Cohorts 3, 4, and 5. Two subjects (1 LY3478045 and 1 placebo) in each cohort will receive a sentinel dose on the same day. After at least 48 hours after dose, the remaining subjects in each cohort may be dosed based on the available safety data.

[figure not shown]

Figure GZKA.1 Illustration of study design for Part A

5.2 Part B

[figure not shown]
Part B will be initiated after assessing safety, tolerability, PK, and PD data through Cohort 3 in Part A.

Multiple-ascending oral doses of LY3478045 will be administered once daily (QD) for 14 days in up to 4 cohorts. Each cohort will consist of 8 subjects. In Cohorts 1 and 3, six subjects will receive LY3478045 and 2 subjects will receive placebo. In Cohorts 2 and 4, six subjects will receive LY3478045 co-administered with a single dose of [CC1] and 2 subjects will receive placebo with a single dose of [CC1]. The maximum dose in males and females will be determined based on the PK analyses from previous cohorts.

A sentinel dosing strategy will be utilized in Cohorts 3 and 4, for which the mean AUC(0-24) is predicted to exceed [CC1] $\mu\text{g}\cdot\text{hr}/\text{mL}$. Two subjects (1 LY3478045 and 1 placebo) in the cohorts for which the mean AUC0-24 is predicted to exceed [CC1] $\mu\text{g}\cdot\text{hr}/\text{mL}$ will receive a sentinel dose on the same day. At least 48 hours after dose, the remaining subjects in each cohort may be dosed based on the available safety data.

Male subjects are allowed in Part B in the cohorts for which the predicted mean exposure AUC0-24 levels for the dose will not exceed [CC1] $\mu\text{g}\cdot\text{hr}/\text{mL}$, 1/10th exposure level observed at [CC1] mg/kg in dogs, which is the lowest dose tested in dogs with no testicular findings, as determined from PK data in Parts A and B.

Female subjects are allowed in Part B in every cohort. The predicted mean exposure AUC0-24 levels for the doses investigated in Part B will not exceed [CC1] $\mu\text{g}\cdot\text{hr}/\text{mL}$, 1/12th exposure level observed at [CC1] mg/kg in dogs, as determined from PK data in Parts A and B.

Abbreviations: AT = atorvastatin; LY = LY3478045; PL = placebo.

Figure GZKA.2 Illustration of study design for Part B

6. TREATMENTS

The following is a list of the study treatment names that will be used in the TFLs.

Part	Study Treatment	Treatment order in TFL

A	Placebo	1
	AA mg LY3478045	2
	BB mg LY3478045	3
	CC mg LY3478045	4
	DD mg LY3478045	5
	EE mg LY3478045	6
B	Placebo QD	1
	Placebo QD + CCI [REDACTED]	2
	FF mg LY3478045 QD	3
	GG mg LY3478045 QD + CCI [REDACTED]	4
	HH mg LY3478045 QD	5
	II mg LY3478045 QD + CCI [REDACTED]	6

7. SAMPLE SIZE JUSTIFICATION

Up to 50 subjects may be enrolled in Part A to ensure that at least 40 subjects complete the study (depending on whether subjects will be enrolled in optional Cohort 5). Up to 40 subjects may be enrolled in Part B to ensure that at least 32 subjects complete the study.

The sample size for Parts A and B of the study was chosen to provide sufficient data for evaluating safety, PK, and/or PD parameters, as well as primary objectives of this study. Subjects who are randomized but not administered treatment, and who are discontinued from the study (providing that discontinuation was not as a result of a safety finding) may be replaced to ensure that enough subjects may complete the study.

8. DEFINITION OF ANALYSIS POPULATIONS

The “Safety” population will consist of all enrolled subjects, whether they completed all protocol requirements.

The “Pharmacokinetic” population will consist of all subjects who received at least one dose of study drug and have evaluable PK data. If a subject has an AE of vomiting that occurs before 2 times the median t_{max} after dosing, then that subject may be excluded from the PK summary statistics and statistical analysis.

The “Pharmacodynamic” population will consist of all subjects who received at least one dose of study drug or placebo and have evaluable PD data.

All protocol deviations that occur during the study will be considered for their severity/impact and will be taken into consideration when subjects are assigned to analysis populations.

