10.1. Sample Size Determination

The sample size for Parts A and B of the study was chosen to provide sufficient data for evaluating safety, PK, and/or PD parameters, as well as primary objectives of this study. For details regarding the number of subjects planned for each part, refer to Section 5.2.

Subjects who are randomized but not administered treatment, and who are discontinued from the study (providing that discontinuation was not as a result of a safety finding) may be replaced to ensure that enough subjects may complete the study.

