10.3. Statistical Analyses

Statistical analysis of this study will be the responsibility of Eli Lilly and Company or its designee.

Pharmacokinetic/PD analyses will be conducted on data from all subjects who receive at least 1 dose of the investigational product and have evaluable PK and PD data.

Safety analyses will be conducted for all enrolled subjects, whether they completed all protocol requirements.

Additional exploratory analyses of the data will be conducted as deemed appropriate.

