CRP	clinical research physician: Individual responsible for the medical conduct of the study. Responsibilities of the CRP may be performed by a physician, clinical research scientist, global safety physician, or other medical officer.
CRU	clinical research unit
CV	cardiovascular
CYP	cytochrome P450
ECG	electrocardiogram
eCRF	electronic case report form
Enroll	The act of assigning a subject to a treatment. Subjects who are enrolled in the study are those who have been assigned to a treatment.
Enter	Subjects entered into a study are those who sign the informed consent form directly or through their legally acceptable representatives.
ERB	ethical review board
FTT	fructose tolerance test
GCP	good clinical practice
GLP	Good Laboratory Practice
HIV	human immunodeficiency virus
IB	Investigator's Brochure
ICF	informed consent form
ICH	International Council for Harmonisation
informed consent	A process by which a subject voluntarily confirms his or her willingness to participate in a particular study, after having been informed of all aspects of the study that are relevant to the subject's decision to participate. Informed consent is documented by means of a written, signed, and dated informed consent form.
interim analysis	An interim analysis is an analysis of clinical study data, separated into treatment groups, that is conducted before the final reporting database is created/locked.
investigational product	A pharmaceutical form of an active ingredient or placebo being tested or used as a reference in a clinical study, including products already on the market when used or assembled (formulated or packaged) in a way different from the authorized form, or marketed products used for an unauthorized indication, or marketed products used to gain further information about the authorized form.
Investigator	A person responsible for the conduct of the clinical study at a study site. If a study is conducted by a team of individuals at a study site, the investigator is the responsible leader of the team and may be called the principal investigator.

KHK	ketohexokinase
legal representative	An individual or judicial or other body authorized under applicable law to consent, on behalf of a prospective subject, to the subject's participation in the clinical study.
MTD	maximum tolerated dose
NAFLD	nonalcoholic fatty liver disease
NASH	nonalcoholic steatohepatitis
NOAEL	no-observed-adverse-effect level

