9.6 Safety and Tolerability Assessments

9.6.1 Adverse events

Where changes in severity are recorded in the Case Report Form (CRF), each separate severity of the adverse event (AE) will be reported in the listings, only the most severe will be used in the

summary tables. A pre-existing condition is defined as an AE that starts before the subject has provided written informed consent and is ongoing at consent. A non-treatment emergent AE is defined as an AE which starts after informed consent but prior to dosing. A treatment-emergent AE is defined as an AE which occurs postdose or which is present prior to dosing and becomes more severe postdose.

All AEs will be listed. Treatment-emergent AEs will be summarized by Part, treatment, severity and relationship to the study drug. The frequency (the number of AEs, the number of subjects experiencing an AE and the percentage of subjects experiencing an AE) of treatment-emergent AEs will be summarized by Part, treatment, Medical Dictionary for Regulatory Activities (MedDRA) version 22.1 system organ class and preferred term. The summary and frequency AE tables will be presented for all causalities and those considered related to the study drug by the investigator. Any serious AEs will be listed.

Discontinuations due to AEs will be listed.

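### The Safety population has no dosing condition, so a randomized but never-dosed subject would lower the treatment-emergent adverse event percentages

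*SAP*

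**What the plan says.** The SAP (section 8) states that the Safety "population will consist of all enrolled subjects, whether they completed all protocol requirements". Protocol 10.3 agrees: "Safety analyses will be conducted for all enrolled subjects, whether they completed all protocol requirements". The glossary in Protocol Appendix 1 fixes the meaning of the key word: "Subjects who are enrolled in the study are those who have been assigned to a treatment".

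SAP 7 and Protocol 10.1 both provide for "Subjects who are randomized but not administered treatment, and who are discontinued from the study". If no safety finding was the cause, such subjects "may be replaced to ensure that enough subjects may complete the study". Under Protocol 5.1, a replacement takes over the treatment assignment of the subject being replaced.

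For adverse events, SAP 9.6.1 says "A treatment-emergent AE is defined as an AE which occurs postdose", and also counts an event already present before dosing that becomes more severe afterwards. The summary includes "the percentage of subjects experiencing an AE) of treatment-emergent AEs will be summarized by Part, treatment" and further categories.

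The Pharmacodynamic population in SAP 8 is defined differently: that "population will consist of all subjects who received at least one dose of study drug or placebo and have evaluable PD data". The Pharmacokinetic population also requires a dose.

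**The concern.** Read together, these definitions put a randomized but never-dosed subject in the Safety population, while the TEAE definition keeps that subject out of the numerator. Any percentage taken over the Safety population is then too low for the treatment concerned.

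TEAE incidence is part of the primary endpoint (Protocol section 4, Table GZKA.1), and each active arm has only 6 subjects, so one extra subject in the denominator is visible in the table.

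The design also offers a route to such subjects. In sentinel cohorts the remaining subjects wait at least 48 hours and are dosed only if the safety data allow it (Protocol 5.1.1 and 5.1.2), and Protocol 7.4.1 allows dosing at a level to be interrupted. Protocol 7.2 does not say when randomization takes place. If a whole cohort were randomized before the sentinel pair is dosed (an assumption), a halt would leave assigned subjects undosed, and the dilution would fall in a cohort that had just shown a safety signal.

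**Working it through.** **Inputs**
- Allocation is 6 active to 2 placebo per cohort, with up to 5 cohorts in Part A and up to 4 in Part B (SAP 5.1, 5.2).
- Part B has two placebo lines in SAP 6, with and without the co-administered drug. Each is read as pooling two cohorts: 2 × 2 = 4 subjects.
- The Part A placebo line has 4 × 2 = 8 subjects, or 5 × 2 = 10 with optional Cohort 5.
- Replacement is optional and goes to the same arm.
- The number of undosed subjects is not stated. I assume 0, 1 or 2 in one treatment line.

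**The plan's own numbers**

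5 × 8 = 40 and 4 × 8 = 32 reproduce the completer targets. The enrollment caps of 50 and 40 leave 50 − 40 = 10 and 40 − 32 = 8 places beyond those targets. This is room for all non-completers, not a forecast of undosed subjects.

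**Formula**

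Let *n* be the planned size, *u* the number undosed, and *x* the dosed subjects with a TEAE.
- Replaced: the true percentage is x/n and the reported one is x/(n + u), so the factor is n/(n + u).
- Not replaced: the true percentage is x/(n − u) and the reported one is x/n, so the factor is (n − u)/n.

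| Treatment line | n | u | Replaced | Not replaced |
|---|---|---|---|---|
| Any | any | 0 | 1 | 1 |
| Active arm | 6 | 1 | 6/7 = 0.857 | 5/6 = 0.833 |
| Active arm | 6 | 2 | 6/8 = 0.750 | 4/6 = 0.667 |
| Part B placebo line | 4 | 1 | 4/5 = 0.800 | 3/4 = 0.750 |
| Part A placebo, 4 cohorts | 8 | 1 | 8/9 = 0.889 | 7/8 = 0.875 |
| Part A placebo, 5 cohorts | 10 | 1 | 10/11 = 0.909 | 9/10 = 0.900 |

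**Illustration with assumed event counts, one undosed active subject**
- Replaced: 3/6 = 50.0% would be reported as 3/7 = 42.9%.
- Not replaced: 3/5 = 60.0% would be reported as 3/6 = 50.0%.

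**The case against.** - **The denominator is inferred.** SAP 9.6.1 names none, SAP 9.1 says only that summaries generally use the relevant population, and SAP 3 leaves table detail to a separate shell document that is not available here. This stands as a limit on certainty. But section 8 is where the population is defined, and shells that divided by dosed subjects would depart from it, so the SAP needs the sentence either way.
- **SAP 8 lets protocol deviations be weighed when subjects are assigned to populations.** That is a partial safeguard. It is discretionary, does not mention dosing, and not being dosed need not be a deviation.
- **The event may be rare.** Subjects in Part A and in Part B Cohorts 1 and 3 are admitted on Day -1 and dosed on Day 1, so late randomization would leave little time for it. This is fair, and the two-undosed row is purely an assumption. Still, both documents provide for the case.
- **Little depends on the percentage.** The number of events and the number of subjects affected appear beside it, all adverse events are listed, and no active-versus-placebo test of TEAE percentages is planned. The escalation rules (Protocol 7.4.1) and study-level triggers (Protocol 8.4) do not use it. All of this stands and is why the point is minor.
- **The two documents agree with each other.** They do, but they agree on a set that does not fit the TEAE definition.
- **Someone given only the Day -2 atorvastatin has received a drug in the study, and the TEAE definition does not say which dose counts.** That is true. However, SAP 6 has no treatment line for such a subject, so a by-treatment table would have to place the subject under a regimen never started. Listings keep the subject's events in view.

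**Conclusion.** The concern holds and is minor. As written, a never-dosed subject belongs to the Safety population but cannot have a TEAE. With one such subject, the reported percentage is 0.857 (replaced) or 0.833 (not replaced) of its true value in an active arm, and 0.800 or 0.750 in a Part B placebo line. Part A placebo is less affected, at 0.875 to 0.909.

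This rests on three assumptions: the Safety population is the TEAE denominator, at least one subject is randomized and never dosed, and the Part B placebo lines each pool two cohorts. If every randomized subject is dosed, nothing changes. Counts, listings, serious adverse event reporting and dosing decisions are unaffected in every case.

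**What to change.** - **SAP 8:** define the Safety population as enrolled subjects who received one or more doses of LY3478045 or placebo.
- **SAP 9.6.1:** state that this population, grouped by treatment received, is the denominator for TEAE percentages. The SAP does not currently say whether safety summaries follow assigned or received treatment, and this settles it.
- **Disposition and listings:** show never-dosed subjects, and any who received only the Day -2 atorvastatin, with their adverse events, so that no safety information is lost. A separate atorvastatin-alone summary is not needed.
- **SAP 11:** record the change, since that section now reports none. Align Protocol 10.3 if the protocol is amended.

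The cost is a sentence in each of SAP 8 and 9.6.1 and an entry in SAP 11. No new data or tables are required, and results change only if an undosed subject occurs.
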